## SCHEMA

[figure not shown]

Figure 1. Study overview.

**Study plan.** The study is an open label, single institution, pilot study to determine the distribution pattern of  $^{89}\text{Zr}$ -panitumumab and panitumumab-IRDye800 in subjects with head and neck squamous cell carcinoma (HNSCC) that undergo surgery with lymphadenectomy of curative intent. 30 mg of panitumumab-IRDye800 will be administered 1-5 days prior to surgery, intravenous (IV) over 15 min followed by an observation period of 30 min.  $^{89}\text{Zr}$ -panitumumab will be systemically injected at a dose of 1.0 mCi +/- 20%, and with a specific activity greater than 200 Ci/mmol at the time of injection. The injected mass dose is less than or equal to 1 mg (7 nmol); the subject will be monitored for 1 hour post-administration. If at any point two subjects in a cohort experience a DLT, then the study will stop and safety data will be reviewed. The medical monitor and safety review will occur independently.

There will be 7 subjects enrolled into each cohort (total of 14 subjects in the study) whereby, based on the preoperative work-up, including a physical exam and evaluation of the pre-existing imaging data, subjects will be assigned to the node negative or node positive group.

**Rationale for the two cohorts.** To ensure the inclusion of sufficient subjects with clinically positive lymph nodes, we created a cohort structure. Including both node-positive and node-negative subjects will ensure that we will have tumor-positive nodes when performing the data analysis. Moreover, by analyzing data from node-positive subjects it will become possible to assess if, in case large lymph node metastasis are present, the tracer(s) can still reach the node or if rerouting (a phenomenon known to happen in sentinel node mapping, i.e., drainage to a “false” sentinel node occurs because the “true” sentinel node cannot be reached). As shown in the study schema, all subjects regardless if enrolled in cohort 1 or 2, will undergo the same treatment, and upon data collection statistical analysis will be performed with the pooled data.

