## **2.4 Study Design**

### **For clinicaltrials.gov and Stanford Clinical Trials Directory compliance:**

- The primary purpose for the protocol is to develop a universal lymph node detection strategy. This study evaluates if systemic injections of Zr-panitumumab in conjunction with panitumumab-IRDye800 can be used to identify tumor-loaded lymph nodes to expand the capabilities of non-invasive and intraoperative cancer imaging.
- The interventional model is **Sequential**.
- There are **2 cohorts**. Both cohorts will receive the same treatment
- The study is **open-label**. No masking is used.
- The study is **non-randomized**.
- The primary outcome is **the number (proportion) of lymph nodes determined to be tumor-positive by histological and/or pathological evaluation that were predicted to be tumor-positive by Zr-panitumumab PET/CT imaging**.
- The secondary outcome is **the number (proportion) of lymph nodes determined to be tumor-positive by histological and/or pathological evaluation that were NOT predicted tumor-positive by Zr-panitumumab PET/CT imaging**.

The study is an open-label pilot study to determine the efficacy of Zr-panitumumab in tumor-loaded node detection in subjects with HNSCC that undergo surgery with curative intent. It is anticipated that 14 subjects will be enrolled into the study. Subjects will be enrolled to the node negative (no suspicion of tumor-positive lymph nodes in the neck; cN0) or node positive (suspicion of tumor-positive lymph

nodes in the neck; cN+) group based on the preoperative work-up, which includes a physical exam and evaluation of the pre-existing imaging data.

All subjects will receive a dose of 30 mg panitumumab-IRDye800. Subjects will subsequently receive 1 mCi +/- 20% of Zr-panitumumab. If at any point after infusion, 2 subjects experience a DLT (Grade 2 or greater toxicity), then the study will stop, and safety data will be reviewed.

The known rate of infusion reactions of panitumumab is 1% (package insert); therefore, we expect a DLT rate of approximately 1% or higher with panitumumab-IRDye800 or Zr-panitumumab. The probability of observing two or more DLTs within a 10-subject cohort (requiring stopping the study) is 0.4%; if the DLT rate is as high as 5%, the probability of 2 or more DLT is 8.6%.

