## **4. TREATMENT PLAN**

### **4.1 Treatment Schedule**

This study will assess a microdose of Zr-panitumumab and an imaging dose of panitumumab-IRDye800 in 14 subjects. The study drugs will be administered on Day 0, and subjects will undergo one Zr-panitumumab PET/CT imaging anytime starting on Day 0 and the Day before Surgery (inclusive).

Subjects enrolled in the dosimetry sub-study will undergo imaging anytime starting on Day 0 and until the day before surgery (inclusive), for a total of three scans; if available, the scans will be performed on Day 0, Day 1 and on the day before surgery.

Subjects will undergo surgical resection at 2 to 5 days after infusion of study drug (see Table 1). Intraoperative and post-operative imaging data will be collected to answer the study objectives. The study will be stopped if any 2 subjects experience a DLT of grade 2 or higher that is likely to be related to the study drugs administered.

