#### **4.4 Definition of Dose-limiting toxicity (DLT) and Cohort Expansion**

Adverse events will be graded according to the CTCAE v5.0 ([https://ctep.cancer.gov/protocolDevelopment/electronic\\_applications/ctc.htm](https://ctep.cancer.gov/protocolDevelopment/electronic_applications/ctc.htm)).

Dose-limiting toxicity will be defined as any Grade 2 or greater toxicity that is determined by the principal investigator to be possibly, probably or definitely-related to study drugs and clinically significant for subjects who received panitumumab-IRDye800 and  $^{89}\text{Zr}$ -panitumumab for this study. Clinically significant is defined based on NCI definition – a result that is large enough to affect a subject's disease state in a manner that is noticeable to the subject and/or caregiver or requires intervention.

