#### **4.5 Study Drug Discontinuation**

Study drug will be discontinued for any of the following:

- Subject withdraws consent for the study
- Death attributed to study drug
- Serious systemic anaphylactic reaction (Grade 3 or higher)
- Any serious rare reactions attributed to study drug

If one of these events occurs, and is a serious adverse event (see Section 7.2), the FDA, IRB and Stanford DSMC will be notified immediately and there will be a comprehensive review of the safety data prior to resuming and further study drug administration.

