### 11.2 Data and Safety Monitoring Plan

The Stanford Cancer Institute Data and Safety Monitoring Committee (DSMC) will be the monitoring entity for this study. The DSMC will audit study-related activities to determine whether the study has been conducted in accordance with the protocol, local standard operating procedures, FDA regulations, and Good Clinical Practice (GCP). This may include annual review of the following types of documents participating in the study: regulatory binders, case report forms, eligibility checklists, and source documents. In addition, the DSMC will regularly (monthly) review any DLTs, serious adverse events, and protocol deviations associated with the research to ensure the protection of human subjects. Results of

the DSMC audit will be communicated to the IRB and the appropriate regulatory authorities at the time of continuing review, or in an expedited fashion, as needed.

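### Section 2.4 gives stopping probabilities for a 10-subject cohort, but the rule covers 14 subjects, and the Schema words the trigger more narrowly than Sections 2.4 and 4.1

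*Combined protocol and SAP*

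**What the plan says.** Section 2.4 (Study Design) sets the DLT rule: "If at any point after infusion, 2 subjects experience a DLT (Grade 2 or greater toxicity), then the study will stop". The next paragraph takes about 1% or higher as the expected DLT rate and gives the rule's operating characteristics: "The probability of observing two or more DLTs within a 10-subject cohort (requiring stopping the study) is 0.4" per cent at 1%, and 8.6% if the rate is 5%.

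Section 4.1 (Treatment Schedule) also counts across the study, for drug-related events: "The study will be stopped if any 2 subjects experience a DLT of grade 2 or higher that is likely to be related".

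The Schema gives the size of the study: "There will be 7 subjects enrolled into each cohort (total of 14 subjects in the study". Its own wording of the trigger is: "If at any point two subjects in a cohort experience a DLT, then the study will stop".

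The synopsis, Table 1, Section 4.1 and Section 12 also give 14 subjects. Both cohorts receive the same treatment.

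**The concern.** The probability sentence in Section 2.4 is the only place where the protocol says how often its DLT rule would stop the study. It uses a sample size that is neither the cohort size (7) nor the study size (14). A committee reading it would see roughly half the stopping chance that the rule in the same section implies.

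The trigger is also not worded alike throughout. With one DLT in each cohort, the rule in Sections 2.4 and 4.1 is met and the Schema's condition is not. Section 2.4 sends readers to the Schema for an overview of the study, so some may take the rule from there.

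**Working it through.** **Inputs.** DLT rates p = 1% and 5%, and the printed 0.4% and 8.6%, from Section 2.4. Study size 14 and cohort size 7, from the Schema. Stopping at 2 DLTs, from the Schema and Sections 2.4 and 4.1. Subjects are taken as independent with a common rate p, and all 14 are dosed unless the rule stops the study. The chance that the rule is ever met then equals the chance of at least 2 DLTs among 14.

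**Formula.** P(X ≥ 2) = 1 − (1−p)^n − n·p·(1−p)^(n−1).

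**Step 1: reproduce the printed figures (n = 10).**
- p = 1%: 1 − 0.90438 − 0.09135 = 0.427%, printed as 0.4%.
- p = 5%: 1 − 0.59874 − 0.31512 = 8.614%, printed as 8.6%.

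Both agree, so the arithmetic is right for n = 10.

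**Step 2: apply the rule in Sections 2.4 and 4.1 (n = 14).**
- p = 1%: 1 − 0.86875 − 0.12285 = 0.840%.
- p = 5%: 1 − 0.48767 − 0.35934 = 15.299%.
- Ratios to n = 10: 0.840/0.427 = 1.97 and 15.299/8.614 = 1.78.

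**Step 3: the Schema's condition taken alone.** For one cohort of 7 the formula gives 0.203% and 4.438%. The chance that at least one of two such cohorts meets it is 1 − (1 − P7)², where P7 is the one-cohort value: 0.406% and 8.679%.

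**Step 4: the case on which the wordings differ.** Exactly one DLT in each cohort has probability [7p(1−p)^6]²: 0.434% and 6.619%. This is the difference between Steps 2 and 3 (0.840 − 0.406 and 15.299 − 8.679, to rounding).

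| Rule | p = 1% | p = 5% |
|---|---|---|
| Printed in Section 2.4 (n = 10) | 0.4% | 8.6% |
| Any 2 of 14 (Sections 2.4 and 4.1) | 0.84% | 15.3% |
| Two in the same cohort, either cohort of 7 (Schema alone) | 0.41% | 8.7% |
| One in each cohort (Schema condition not met) | 0.43% | 6.6% |

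**The case against.** The best reply concerns weight. The sentence states its own n, so a careful reader can see the mismatch. The figures set no dose, threshold or sample size; the sample size argument in Section 12 rests on lymph nodes. The any-2 rule also stops sooner than the printed numbers suggest, which protects subjects. All of this stands, and it keeps the severity low.

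A second reply is that the printed figures nearly match the Schema's condition over both cohorts (0.41% and 8.7%). That match is a coincidence: the text says 10 subjects, and 8.679% rounds to 8.7%, not 8.6%. It does show that the two parts of the point cannot both apply at full strength. If the Schema governed, the printed numbers would be nearly right. If Sections 2.4 and 4.1 govern, the trigger is clear and the numbers are wrong.

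A reader might infer that the protocol contains opposing stopping rules, or that staff would carry on dosing after one DLT in each cohort. The documents do not support that. Every event that meets the Schema's condition also meets Section 4.1, no text directs dosing to continue, and anyone following all three places stops at any 2 subjects. The one-per-cohort case makes up 52% (0.434/0.840) and 43% (6.619/15.299) of the stops under the any-2 rule, but those shares would be missed only if the Schema alone were read as exhaustive.

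Other safeguards help. After certain single drug-attributed events that are also serious adverse events, Section 4.5 says "there will be a comprehensive review of the safety data prior to resuming and further study drug administration". Section 11.2 says "the DSMC will regularly (monthly) review any DLTs, serious adverse events, and protocol deviations". The Schema also calls for independent medical-monitor and safety review. It would go too far to say that these confine the ambiguity to non-serious Grade 2 events: Section 4.5 does not clearly cover a related, non-serious Grade 3 event, and the documents give no split by grade.

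**Conclusion.** The point holds as a low-severity correction. Under the rule in Sections 2.4 and 4.1, the probability of stopping is 0.84% at a 1% DLT rate and 15.3% at 5%, so the printed figures are low by factors of about 2.0 and 1.8. This rests on independent subjects, a common DLT rate and the planned 14 subjects. The Schema's wording is loose rather than contradictory: it is narrower than the other two sections and leaves one case unclear to someone who reads it alone.

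Two neighbouring matters are separate and should not be folded in. Section 4.1 counts events likely to be related, while Section 4.4 counts events "determined by the principal investigator to be possibly, probably or definitely-related to study drugs and clinically significant"; aligning them could change which events count towards stopping and needs its own decision. The 1% rate is described in Section 5.2.2.2 as Grade 1 infusion reactions, below the DLT threshold. That bears on the choice of p, not on the error in n.

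**What to change.** In Section 2.4, replace the probability sentence with: *With 14 subjects, the probability of two or more DLTs is 0.84% if the DLT rate is 1% and 15.3% if it is 5%.* In the Schema, delete the words 'in a cohort', so that the Schema, Section 2.4 and Section 4.1 all count any 2 of the 14 subjects.

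The cost is one restated sentence and one deletion. The only downside is that the stated stopping probabilities are higher. Stopping after one DLT in each cohort is not a new burden, because Sections 2.4 and 4.1 already require it. Dose, sample size and procedures are unaffected.

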**Table 1: Dosing Schedule**

No. of subjects	14
Dose of panitumumab-IRDye800	30 mg
Dose of Zr-panitumumab	1.0 mCi, allowable range 0.8 to 1.2 (29 to 44 Mbq)
Specific Activity of Zr-panitumumab	>200 Ci/mmol
PET imaging post-infusion*	Day 0 to the Day before Surgery
Timing of surgical procedure post-infusion	Day 2 to 5 post-infusion

Each subject will be followed for 30 days following the last dose of study medication.

**Outcome measures to answer the primary and secondary objectives set:**

Preoperative data:

1. Collect safety data on tracer-infusion.
2. The number and location of F-FDG-PET positive nodes.
3. The number and location of Zr-panitumumab-PET positive nodes.

Intraoperative data:

4. The number and location of Zr-panitumumab-PET positive nodes.
5. The number and location of panitumumab-IRDye800 positive nodes.

Post-operative data:

6. Collect safety data in follow-up (up to 30 days post-infusion).
  - a. This includes tests and observations to identify both acute and late-treatment specific toxicity: vital signs; physical exam; toxicity grading; assignment of performance status; hematology; and blood chemistries (basic metabolic profile to include magnesium and phosphorus). NCI Common Toxicity Criteria v5.0 will be used for grading of toxicity.
7. Determine *ex vivo* fluorescence imaging information on panitumumab-IRDye800 (method described previously in (21)).
8. Determine the histo-pathological status of the primary tumor.
9. Determine the histo-pathological status of the lymph nodes: tumor-positive (isolated tumor cells, micro- or macro-metastasis) or tumor-negative.
10. Determine, using immunohistochemistry, on the surgically excised tissue specimens:
  - a. Tumor tissue viability
  - b. EGFR expression
  - c. Vessel density

We have previously described the methods for analysis in (26).

For qualification and quantification of the fluorescence signal and the radioactive signal, we follow the following rules:

- *Intraoperative fluorescence assessment of panitumumab-IRDye800:*

There will be no set level of fluorescence whereby we consider tissue positive or negative; it is based on operator's impression.

- *Ex vivo fluorescence assessment of panitumumab-IRDye800:*

From the fluorescence images taken in the operation room, we will calculate tumor-to-background ratios (TBRs) as such to define a more quantitative read-out (similar to as described in the IRB-35064 study). Based on the current data available from our IRB-35064, in our 50 mg cohort, we found an average TBR of  $6.53 \pm 1.2$ , a sensitivity of  $89 \pm 5.1\%$ , a specificity of  $92 \pm 3.5\%$  (AUC:  $0.93 \pm 0.05$ ). The NPV and PPV were  $94 \pm 2.8\%$  and  $92 \pm 9.5\%$ , respectively. We will extrapolate these findings to the current study to further validate the findings from our phase I study (IRB-35064).

- *Radioactive assessment of Zr-panitumumab:*

Following the standard of care evaluation of PET/CT scans, maximum standard uptake values ( $SUV_{max}$ ) will be calculated for the accumulation of Zr-panitumumab in tumor tissue and/or lymph nodes. As background reading, the  $SUV_{max}$  of the mediastinum will be determined.

Tentative cutoff for 'imaging positive': an  $SUV_{max}$  value of the lymph nodes of minimally  $1.4 \times$  the background (mediastinum). In all cases, (histo-) pathology serves as the gold standard for "true" positive / negative lymph nodes. Subsequently a ROC curve will be generated whereby we will select

the point of highest specificity and sensitivity and from there we will determine if our tentative cutoff was valid or if we need to adjust.

- *Comparison fluorescence and radioactivity-based findings:*

All tissues that will be excised during surgery will be evaluated for the presence of radioactivity and fluorescence and scored as such being positive / negative. Evaluated tissues are either 1) fluorescent only; 2) radioactive only; 3) both radioactive and fluorescent; or 4) neither radioactive nor fluorescent. This will be done quantitatively (Y/N approach) and qualitatively (see above).

- Because the antibody is the same, only the label (IRDye800 or 89-Zr) differs, we expect that tissue samples that are radioactive are also fluorescent and vice versa. However, this is something that will be investigated in this study.

Statistical considerations are described in detail in Section 11.

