For an overview of the proposed study, see Study Schema (page 9), and the dosing schedule below. Briefly, subjects will undergo F-FDG-PET prior to study enrollment, as is standard of care. Administration of panitumumab-IRDye800 will occur by IV over 15 minutes, followed by a 30-minute observation period. Administration of Zr-panitumumab will occur by IV, per radioactive drugs administration policies. The subjects will be observed for 1 hour following the Zr-panitumumab injection.

After infusion of study agents on Day 0, subjects will undergo Zr-panitumumab PET/CT imaging. One scan will be performed at any time starting on Day 0 (after end of observation period post Zr-panitumumab administration) and until the day before surgery (inclusive). Subjects enrolled in the dosimetry sub-study will undergo three scans, performed at any time starting on Day 0 (after end of observation period post Zr-panitumumab administration) and until the day before surgery. If available, the scans will be performed on Day 0, Day 1 and on the day before surgery.

Subjects will undergo surgical resection 2-5 days after infusion of study drugs. Imaging will be performed intraoperatively using a novel beta probe and/or high-energy gamma probe (see Appendix C for a list of devices) and the optical imaging devices (see Appendix B for a list of devices), to assess the tumor and lymph node(s) prior to resection, and the wound bed after surgical removal. The surgery will be conducted in the standard of care, and the surgeon will not use the imaging data to make decisions.

*Ex vivo*, imaging of the specimens prior to pathological assessment will be performed using non-invasive imaging modalities that do not violate or destroy the tissue. These may include beta probe and/or high-energy gamma probe, an open-field imaging system, a closed-field imaging system and a fluorescence flatbed scanning device (see Appendix B and C for a list of devices). Additionally, a closed Cherenkov imaging system may be used to image the specimen after removal (see Appendix C). Methods have been described in detail in the literature (20-25).

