### **Dosimetry**

Previously, for the antibody trastuzumab, it has been shown that when giving a pre-dose of cold (i.e. not radiolabeled) trastuzumab, prior to giving the radiopharmaceutical, the toxicity to the liver (and other organs) was found to be significantly lower resulting in the ability to go up on the dose of the radiopharmaceutical given, improving the preoperative image quality. For Zr-panitumumab, there is little data on dosimetry. At the moment one publication reporting on data in 3 patients (28) whereby it was shown that upon giving a ~1 mCi dose, there's relative high toxicity to the organs, in particular the liver (28).

In our current study, in a subset of 3-5 subjects we will collect dosimetry data by assessing the biodistribution of Zr-panitumumab over time as such to determine the toxicity of Zr-panitumumab to the organs. To obtain dosimetry data, at various time points after injection of Zr-panitumumab, PET/CT scans are to be acquired. The minimum number of PET/CT scans needed is three.

For the current study, these three PET/CT scans will be obtained between the end of observation period after the Zr-panitumumab infusion on Day 0 and the day before surgery (inclusive). If available, the scans will be performed on Day 0, Day 1 and on the day before surgery.

For each patient, on the acquired PET/CT scans, volumes of interest (VOIs) will be drawn around the organs, tumor and lymph nodes. Subsequently, the total activity in each VOI will be recorded in units of Becquerel (Bq). Time activity curves (TACs) will be generated and then integrated to obtain the number of disintegrations (NDs) in each region. Hereafter the data will be loaded into dedicated software (e.g., OLINDA/EXM code (version 1.1.) after which the absorbed dose (in mGy/MBq) to each VOI can be determined. The internal dosimetry calculation model will be implemented following the Committee on Medical Internal Radiation Dose (MIRD) guidelines.

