## **10. MEASUREMENTS**

### **10.1 Primary Outcome Measure**

**The number (proportion) of lymph nodes determined to be tumor-positive by histological and/or pathological evaluation that were predicted to be tumor-positive by  $^{89}\text{Zr}$ -panitumumab labeling.**

We will compare the number and location of  $^{18}\text{F}$ -FDG-avid nodes within the regional lymphatics to the number and location of  $^{89}\text{Zr}$ -panitumumab-avid nodes in relation to the postoperative neck dissection histopathology (gold standard).

**Outcome Measure:** Preoperatively, the location and number of  $^{18}\text{F}$ -FDG-avid nodes as well as the number and location of  $^{89}\text{Zr}$ -panitumumab-avid nodes will be determined by 2 board-certified Nuclear Medicine physicians ([name] and [name]). Once all radioactive and fluorescent nodes are removed intraoperatively, standard of care will be

performed via completion neck dissection. The excised tissue specimens will be sent to pathology where the tumor status of the lymph nodes will be determined (histology serves as our gold standard). This will allow us to determine true and false positive and negative tumor values for Zr-panitumumab and F-FDG in identifying the tumor-loaded lymph nodes.

**Time Frame:** Final false positive and negative rate, sensitivity and specificity of sentinel node detection using Zr-panitumumab can be determined towards the completion of the trials (once all subjects have been included and all the data has been collected).

**Safety Issue:** No

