Following the standard of care evaluation of PET/CT scans, maximum standard uptake values ( $\text{SUV}_{\text{max}}$ ) will be calculated for the accumulation of  $^{89}\text{Zr}$ -panitumumab in tumor tissue and/or lymph nodes. As background reading, the  $\text{SUV}_{\text{max}}$  of the mediastinum will be determined.  
Tentative cutoff for 'imaging positive': an  $\text{SUV}_{\text{max}}$  value of the lymph nodes of minimally  $1.4 \times$  the background (mediastinum). In all cases, (histo-) pathology serves as the gold standard for "true" positive / negative lymph nodes. Subsequently an ROC curve will be generated whereby we will select the point of highest specificity and sensitivity and from there we will determine if our tentative cutoff was valid or if we need to adjust.
- *Comparison fluorescence and radioactivity-based findings:*  
All tissues that will be excised during surgery will be evaluated for the presence of radioactivity and fluorescence and scored as such being positive / negative. Evaluated tissues are either 1) fluorescent only; 2) radioactive only; 3) both radioactive and fluorescent; or 4) neither radioactive nor fluorescent. This will be done quantitatively (Y/N approach) and qualitatively (see above).
  - Because the antibody is the same, only the label (IRDye800 or  $^{89}\text{Zr}$ ) differs, we expect that tissue samples that are radioactive are also fluorescent and vice versa. However, this is something that will be investigated in this study.

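### The background for calling a node 89Zr-positive is the SUVmax of a mediastinal region whose size and site are not fixed, so calls near the cut-off depend partly on how the region is drawn

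*Combined protocol and SAP*

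**What the plan says.** Section 2.4 (radioactive assessment of 89Zr-panitumumab) sets the background: "As background reading, the $SUV_{max}$ of the mediastinum will be determined". A node is tentatively positive at an SUVmax "value of the lymph nodes of minimally $1.4 \times$ the background (mediastinum"). Section 12, under descriptive statistics, repeats both rules, again with the SUVmax "of the mediastinum will be determined". After an ROC curve against pathology, "we will determine if our tentative cutoff was valid or if we need to adjust".

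This is the only numerical 89Zr-PET positivity rule in the plan. The measures built on 89Zr-PET calls are the primary sensitivity and specificity, the comparison with FDG, the false-negative odds and the NPV.

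The rest of the plan does not define the region:
- Section 10.1 says that the avid nodes "will be determined by 2 board-certified Nuclear Medicine physicians", without a rule for the mediastinal region.
- The dosimetry text in Section 2.4 says "volumes of interest (VOIs) will be drawn around the organs, tumor and lymph nodes". It applies to 3 to 5 subjects, records total activity, and gives no mediastinal volume or site.
- No reconstruction or noise standard is stated, nor whether the blood pool or the whole mediastinum is read.

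Two other provisions affect count noise. Table 1 allows "1.0 mCi, allowable range 0.8 to 1.2 (29 to 44 Mbq"), and Section 2.4 says of the PET/CT, "One scan will be performed at any time starting on Day 0", up to the day before surgery.

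**The concern.** A background value should estimate typical uptake in reference tissue. The hottest voxel of a region does not. Its expected value grows with the number of voxels drawn and with image noise, and a single avid mediastinal focus can replace it. Two readers who draw different regions on the same scan can therefore set different cut-offs for the same node.

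One denominator serves all of a subject's nodes, about 30 on the plan's own average, so an error in it shifts that subject's calls in one direction. At the planned prevalence of 7.5%, 420 nodes contain about 420 x 0.075 = 31.5 positives. Each changed call on a positive node then moves sensitivity by about 1/31.5, or 3 percentage points.

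**Working it through.** **The plan's own figures.** The 1.4 multiple has no derivation to reproduce. The node counts do reproduce: 14 x 30 = 420, and 420 / (1 + 29 x 0.005) = 366.8, the stated 367. The power statement takes node calls as given and does not change with this point.

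**Assumptions, not in the documents.** Independent Gaussian voxels with mean 1 and coefficient of variation CV of 5, 10 or 20%; mediastinal regions of n = 20, 100 or 1000 independent voxels; node SUVmax taken over 5 voxels with the same CV.

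**Step 1: effective cut-off.** Expected maximum / mean = 1 + CV x e(n), where e(n) is the expected maximum of n standard normal values: 1.867, 2.508 and 3.241 for n = 20, 100 and 1000. The effective cut-off, in multiples of mean background, is 1.4 x (1 + CV x e(n)):

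| CV | n = 20 | n = 100 | n = 1000 |
|---|---|---|---|
| 5% | 1.53 | 1.58 | 1.63 |
| 10% | 1.66 | 1.75 | 1.85 |
| 20% | 1.92 | 2.10 | 2.31 |

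**Step 2: which nodes are affected.** Simulated probability of a positive call, with noise in both node and mediastinum, by true node-to-mean-background ratio:

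| True ratio | CV | n = 20 | n = 100 | n = 1000 |
|---|---|---|---|---|
| 1.6 | 10% | 83% | 61% | 27% |
| 1.6 | 20% | 58% | 29% | 8% |
| 2.0 | 10% | at least 99% | at least 99% | at least 99% |
| 2.0 | 20% | 97% | 90% | 70% |
| 2.5 | 10 or 20% | at least 99% | at least 99% | at least 99% |

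At CV 5%, the node at 1.6 ranges only from 99% (n = 20) to 87% (n = 1000).

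**Step 3: how far noise can differ between subjects.**
- Activity range alone: 1.2 / 0.8 = 1.5-fold in counts, so the square root of 1.5 = 1.22-fold in relative noise. At n = 100, CV 10% against 12.2% moves the effective cut-off from about 1.75 to 1.83.
- Adding decay from Day 0 to Day 4 with the stated half-life of 78.4 hours: 2^(96/78.4) = 2.34; 1.5 x 2.34 = 3.5-fold in counts, or 1.87-fold in noise. At n = 200, CV 10% against 18.7% moves the cut-off from about 1.78 to 2.12. Counting from Day 1, the noise ratio is about 1.7-fold. This takes physical factors only, with all else equal.

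**Step 4: a mean denominator.** With SUVmean, the expected cut-off is 1.40 x mean at any region size or noise level. Its SD is 1.4 x CV / sqrt(n); at CV 10% and n = 100 this is 0.014. But node SUVmax is still a maximum. With 1.4 unchanged and n = 100:

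| True ratio | CV 10% | CV 20% | With SUVmax denominator |
|---|---|---|---|
| 1.0 | 0% | 11% | 0% at both |
| 1.2 | 22% | 67% | 0.1% or less |

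The plan implies 420 x 0.925 = 388.5 negative nodes. If all sat at background level in scans with CV 20%, 11% would be about 43 noise false positives.

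**The case against.** The strongest case for leaving the rule alone has four parts.

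- **The cut-off is tentative and is checked by ROC.** This largely answers the average upward shift: a constant scale factor is absorbed when the multiple is re-selected. It does not answer variation in the denominator from subject to subject or reader to reader, because one multiple is applied to all.
- **Node SUVmax is also a maximum, so noise partly cancels.** True, and Step 2 includes it. Region size does not cancel. Step 4 shows that dropping the cancelling denominator has a price in specificity.
- **The magnitude rests on chosen inputs.** This stands. CV, voxel counts and independence are assumptions, and a node at 1.6 sits where the effect is largest. The plan gives no distribution of node ratios, so the number of nodes near the cut-off is unknown.
- **Maximum-to-maximum is an analyst's choice, read by two board-certified physicians in line with standard-of-care evaluation.** Expertise helps, but no written instruction makes two readers draw the same region.

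A reader might infer that the allowed activity range alone makes noise differ widely between subjects. It gives only about 1.2-fold; larger contrasts need scan day as well, and scan day also changes true blood-pool level, which is a separate matter. A reader might also infer that swapping in SUVmean at 1.4 cures the problem. Step 4 shows that it does not.

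**Conclusion.** The point holds for nodes near the cut-off. The plan's background statistic depends on an undefined region and on noise, and the resulting error is shared by all of a subject's nodes. That direction follows from the rule itself.

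The size is not established. Under CV of 5 to 20% and 20 to 1000 voxels, the effective cut-off lies at about 1.5 to 2.3 times mean background. Clearly avid nodes are little affected: at 2.5 times mean they stay positive in every setting tried, and at 2.0 times mean they do so at CV 10%. After the ROC step, only scatter between subjects remains.

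It would be tempting to read the Step 2 probabilities as the loss of sensitivity to expect, or to conclude that 89Zr-PET accuracy in this trial is biased by a known amount. The documents support neither, since they give no noise level, region size or distribution of node uptake. This is a worthwhile, inexpensive change to a stated measurement rule; it does not invalidate the primary analysis.

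**What to change.** In Sections 2.4 and 12:

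1. Define background as the SUVmean of a fixed-volume region in the mediastinal blood pool, with the same volume in every subject and placed away from focal uptake.
2. Use node SUVmax divided by that SUVmean for both the positive/negative calls and the ROC curve.
3. Re-declare the tentative multiple on the new scale, with its reasoning, before any reads are compared with pathology. Do not keep 1.4 by default: in Step 1 the present rule already corresponds to more than 1.5 times mean background.

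If the sponsor prefers to keep SUVmax, the minimum is to fix the region's volume and site.

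The cost is two sentences and one line of reading instructions, with no new scan or reader. For scans already acquired, the ratio can be recomputed from stored images by readers unaware of the pathology. There are two downsides: the multiple must be justified afresh, and some noise dependence remains through node SUVmax.
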